administered starting at Cycle 8 for up to a total of 24 cycles. Cycle 1 will consist of 35 days. Cycles 2 and beyond will be 28 days. The safety assessment (DLT) period begins at the start of treatment and extends to the end of Cycle 3.

Patients with RT will receive APR-246 administered IV at the assigned cohort dose with standard doses of venetoclax and rituximab. Dose escalation will proceed in a standard 3 + 3 dose escalation design.

The intended three dose levels of APR-246 are: 1.5 g/day, 3.0 g/day, and 4.0 g/day administered as an IV infusion over 6 hours. The dose escalation will proceed until a pharmacologically active dose level is achieved. It will be stopped if the maximum tolerated dose (MTD) is reached at a dose level below the maximum planned dose of 4.0 g/day. For the determination of MTD the following rules will be applied:

- Three patients will be enrolled to Dose Level 1.
- If 0 patients out of 3 experience a DLT at Dose Level 1 (1.5 g/day of APR-246), the dose will advance to the next level (Dose Level 2, 3.0 g/day).
- If 1 of the first 3 patients at Dose Level 1 experiences a DLT, 3 additional patients will be recruited and treated at the same dose level (1.5 g/day of APR 246).
- If ≥ 2 patients out of 3-6 patients in a cohort experience a DLT at Dose Level 1 (1.5 g/day of APR-246), the study will temporarily discontinue enrollment and the Data Review Team (DRT) will consider further enrollment and possible dose/schedule adjustments.
- If < 2 patients out of 6 experiences a DLT at Dose Level 1 (1.5 g/day), dose escalation will proceed to the next cohort level (Dose Level 2, 3.0 g/day).
- For each cohort, if there are 0 DLTs in the first 3 patients enrolled, the cohort will advance to the next level. If there is 1 DLT in the first 3 patients enrolled to a cohort, the cohort will enroll an additional 3 patients. If there are ≥ 2 DLTs in a cohort, the prior lower dose level will be declared the MTD.
- If there are ≤ 1 DLT in the first 3 patients enrolled at Dose Level 3, 4.0 g/day APR-246, the study will enroll 3 additional patients at Dose Level 3. If there are ≤ 1 DLTs in 6 patients enrolled at Dose Level 3, 4.0 g/day APR-246 will be declared the MTD.

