Upon determination of the pharmacologically active dose or MTD, or when the maximally intended dose is reached, up to 10 additional patients may be enrolled at this dose level to confirm the assessment and to collect additional safety, PK and PD data to aid in determining the recommended dose of APR-246 in combination with venetoclax and rituximab.

Table 3. APR-246 Dose Levels

Dose Modification	APR-246 Dose
Dose Level 1	APR-246 1.5 g/day 0.5 g (for first 45 minutes) + 1.0 g (for 5 hours 15 minutes)
Dose Level 2	APR-246 3.0 g/day 1.0 g (for first 45 minutes) + 2.0 g (for 5 hours 15 minutes)
Dose Level 3	APR-246 4.0 g/day 1.33 g (for the first 45 minutes) + 2.66 g (for 5 hours 15 minutes)

Prior to initiation of study treatment with APR-246 administered IV in combination with venetoclax and rituximab (during treatment cycles 2-7), patients will receive APR-246 alone on Day 1 and Day 2 of the 7-day monotherapy lead-in period, during which PK and PD of APR-246 following IV and PO administration will be evaluated. On Day 1 of the monotherapy lead-in period, APR-246 will be administered IV at the assigned cohort dose. On Day 2, APR-246 will be administered PO at the dose of 500 mg. This dose may be increased based on emerging PK data to determine dose linearity after oral dosing. Patients will be required to fast for at least 10 hours prior to APR-246 PO administration. Furthermore, a sub-group of patients may receive an oral dose of APR-246 in combination with a standard high-fat meal to determine the effect of food on APR-246 absorption.

Additional dose levels may be explored if warranted based on emerging DLT, safety, PK, and/or PD data. In addition, patients who have received at least 3 cycles of therapy at the assigned dose cohort level may advance to the next higher dose level once the next higher dose level has been declared safe by the DRT.

Responses will be assessed according to response criteria for RT ([Appendix V](#)) via blood, BM, and imaging (positron emission tomography [PET]/computed tomography [CT]). Response assessments are to be performed every 3 cycles and PET-CT scanning is recommended. For patients who achieve CR, imaging may be omitted, and minimal residual disease (MRD) assessment will be completed using flow cytometry and/or molecular techniques from the BM and/or peripheral blood.

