5.1.5 Recommended Dose of APR-246

The recommended dose of APR-246 in combination with venetoclax and rituximab represents the dose of APR-246 at or below the maximum intended dose, or the MTD, that results in the greatest apoptosis of circulating malignant cells in the monotherapy cycle.

The MTD of APR-246 will be defined as the dose at which <2 out of 6 patients experience DLT during the defined safety assessment period after administration of APR-246 in combination with venetoclax and rituximab. Up to 10 additional patients may be enrolled at the MTD, and at prior dose levels, to confirm the confidence at that dose level.

A DRT consisting of the Medical Monitor, Site Principal Investigators, and other clinical research personnel that the Sponsor may deem appropriate, will hold Data Review Meetings (DRMs) on an

interim basis at a frequency dependent on study accrual. At these meetings, the DRT will review any AEs, DLTs, and any available PK and PD data and make recommendations regarding the optimal dose of APR-246. All accumulated safety data will be discussed during DRMs. The optimal dose of APR-246 will be based upon the MTD and upon all accumulated safety data, PK/PD data, and preliminary efficacy data.

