7.4 Pharmacokinetic and Pharmacodynamic Evaluation

APR-246 will be administered in a 7-day monotherapy cycle on Days 1 and 2, via IV and PO route, respectively. PK samples for APR-246 measurements will be taken on Day 1 pre-dose, at the end of the infusion and 1, 2 and 4 hours after the end of the infusion, and 24 hours after the end of the infusion prior to APR-246 PO administration on Day 2, as well as 0.5, 1, 1.5, 2, 3, 4, 6, 10 and 24 hours after the oral administration on Day 2. Following review of the initial PK profiles after oral administration, the PK sampling scheme will be reviewed and optimized. Unnecessary samples will be removed from the schedule and sampling times changed (the total number of samples specified below will not be exceeded).

Blood samples for PD markers and GSH will be collected as follows: on Day 1 pre-dose and 4 hours after the end of the infusion; on Day 2 prior to oral administration as well as 10 and 24 hours after the oral administration.

In addition, blood samples for PD and GSH markers will be collected on Cycle 1 Day 1 pre-dose and 4 hours after the end of the infusion.

Table 18: PK, PD, and Glutathione Blood Sampling Timepoints for APR-246

PK and PD Blood Sampling Timepoints	APR-246 PK and PD Sample Collection										
	APR-246 Monotherapy Lead-In Period						Cycle 1	Cycle 2		Cycles 3+	
	D1 ^a		D2 ^b		D3		D1	D 1	D 8	D 15	D1
	PK	PD	PK	PD	PK	PD	PD	PK	PK	PK	PK
Prior to APR-246 administration ^{b,c}	×	× ^d	× ^b	× ^d	× ^c	× ^d	× ^d	×	×	×	
After APR-246 administration (<5 min after end of IV infusion [EOI])	×							×	×	×	×
0.5 h after APR-246 administration			×								
1 h (±5 min) after APR-246 administration	×		×					×	×	×	
1.5 h (±5 min) after APR-246 administration			×								
2 h (±5 min) after APR-246 administration	×		×								
3 h (±15 min) after APR-246 administration			×								
4 h (±15 min) after APR-246 administration	×	× ^d	×				× ^d				
6 h (±15 min) after APR-246 administration			×								
10 h (±1 h) after APR-246 administration			×	× ^d							

^a PK samples are collected at time points related to IV administration of APR-246 on Day 1 of monotherapy lead-in period

^b PK samples are collected at time points related to PO administration of APR-246 on Day 2 of monotherapy lead-in period with the exception of the pre-dose sample collected 24 h after IV administration of APR-246 on Day 1 (prior to PO administration of APR-246 on Day 2)

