8.1 Sample Size

A total of up to 48 evaluable patients will be included in the study.

Patients with RT will be enrolled and receive APR-246 at the assigned dose cohort level. Dose escalation will proceed in a 3 + 3 design. Cohorts will consist of 3-6 patients and 10 additional patients may be enrolled at the MTD. Approximately 6 + 6 + 6 (18) DLT evaluable patients will be enrolled. In the event Dose Level 3 is declared the MTD, up to 10 additional patients may be enrolled at Dose Levels 1 and 2 to gain additional safety, PK, and/or PD data to help define the recommended dose of APR-246 in this combination.

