8.8 Pharmacodynamic Analysis

PD analysis will be conducted using flow cytometry of circulating CLL/RT cells before and after treatment with APR-246 during monotherapy and the first day of combination treatment ramp-up to assess viability and apoptosis. Descriptive statistics (mean, standard deviation, CV% mean, geometric mean, CV% geometric mean) will be utilized to compare the post- and pre-treatment samples and the differences at each dose cohort level will be tested for relationship to dose.

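### Section 4.1 lets the 10-patient expansion open on triggers that need no DLT results, up to about 83–90 days before the latest patient's DLT window closes, while other sections place it at the MTD or lower levels

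*Combined protocol and SAP*

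**What the plan says.** Section 4.1, repeated in the synopsis under Study Design, says that "The dose escalation will proceed until a pharmacologically active dose level is achieved", sets out the 3+3 rules, and then describes the expansion of the level in question: "Upon determination of the pharmacologically active dose or MTD, or when the maximally intended dose is reached, up to 10 additional patients may be enrolled". The three triggers are alternatives. No DLT condition is attached to the first or the third, and no threshold defines a pharmacologically active dose.

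The PD data come early. Section 8.8 has flow cytometry "before and after treatment with APR-246 during monotherapy and the first day of combination treatment ramp-up". Section 7.4 gives the lead-in times: Day 1 before dosing and 4 hours post-infusion, then "on Day 2 prior to oral administration as well as 10 and 24 hours after the oral administration". It adds a pre-dose and a 4-hour sample on Cycle 1 Day 1.

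The DLT data come late. Section 4.1 states: "The safety assessment (DLT) period begins at the start of treatment and extends to the end of Cycle 3". Section 5.1.4 puts this at up to 91 days.

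Three other places describe the same 10 patients differently:
- Section 8.1: "Cohorts will consist of 3-6 patients and 10 additional patients may be enrolled at the MTD". It also allows Dose Levels 1 and 2 if Dose Level 3 is the MTD.
- The synopsis sample-size paragraph says the same in substance.
- Section 5.1.5 allows them at the MTD and at prior dose levels. It defines the MTD by DLTs in fewer than 2 of 6 patients over the whole safety assessment period.

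**The concern.** One primary endpoint is the highest tested dose with a DLT rate below 33%, and it is judged over a period that ends with Cycle 3. Two of the three expansion triggers do not ask for that result. A site or the Data Review Team (DRT) following Section 4.1 could enrol the largest single block of patients at a level while its escalation cohort is still inside the DLT window. One following Section 8.1 could not.

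The protocol does write a safety condition for a smaller step. A patient already on treatment may move up only when the DRT has found the next level safe (in at least 3 patients, according to the synopsis). No such condition is written for 10 new patients.

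At stake are avoidable exposure, and safety, PK and PD data gathered, at a level that the DLT rule then rejects.

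**Working it through.** **1. The plan's own figures.** The sample size reproduces: 3 × 6 + 10 + 2 × 10 = 48. The stated DLT window is 7 + 84 = 91 days, where 84 = 3 × 28. Section 4.1 gives Cycle 1 as 35 days and later cycles as 28, so the end of Cycle 3 is 7 + 35 + 28 + 28 = day 98. The two differ by 7 days. Both are carried below.

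**2. Lead of the PD trigger.** Cycle 1 Day 1 is study day 7 + 1 = 8. Days left in that patient's window:
- to day 91: 91 − 8 = 83
- to day 98: 98 − 8 = 90

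If the lead-in samples alone were used (last on day 3), the figures are 88 and 95. Table 17 also appears to mark PD on Cycle 1 Day 2, unlike Sections 7.4 and 8.8; that sample would give 82 and 89. Assay turnaround is not stated and must be subtracted.

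**3. The 'reached' trigger.** If it means that the top level has opened, it can be met on day 1, with 91 − 1 = 90 or 98 − 1 = 97 days left. If it means that the level has been cleared, there is no lead, but the trigger then repeats the MTD trigger, because at most 1 DLT in 6 patients at 4.0 g/day already makes that dose the MTD.

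**4. How often the rule would reject a level.** The documents give no DLT rate, so p is assumed. Under Section 4.1 a level fails at 2 or more DLTs.
- Dose Levels 1–2 (pass on 0/3, or on 1/3 then 0/3): 1 − [(1−p)³ + 3p(1−p)² × (1−p)³]. At p = 0.33 this is 1 − [0.301 + 0.444 × 0.301] = 0.57.
- Dose Level 3 (always 6 patients unless 2 DLTs occur in the first 3): 1 − P(Bin(6, p) ≤ 1). At p = 0.33 this is 1 − [0.090 + 0.267] = 0.64.

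| Assumed p | Levels 1–2 | Level 3 |
|---|---|---|
| 33% | 0.57 | 0.64 |
| 40% | 0.69 | 0.77 |
| 50% | 0.83 | 0.89 |

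**5. Expansion patients dosed before the window closes.** Accrual and turnaround are assumed: r = 0.5 to 4 patients a month, evenly spaced, and a PD result 14–28 days after the third patient's 7-day lead-in. The trigger T then falls on day 21–35 of that patient's clock. Number dosed = min(10, r × (W − T)/30.4), where W is the window length.

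| r per month | W = 91 | W = 98 |
|---|---|---|
| 0.5 | 0.9–1.2 | 1.0–1.3 |
| 1 | 1.8–2.3 | 2.1–2.5 |
| 2 | 3.7–4.6 | 4.1–5.1 |
| 4 | 7.4–9.2 | 8.3–10 |

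These are upper bounds, because a level fails at its second DLT, which may come before the window closes.

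**6. Cohort patients who have finished their window at the trigger.** At 2 a month or faster, 0 of 3 under either window. At 1 a month, 0 of 3, except 1 of 3 with 91 days and a 28-day turnaround (60.8 + 35 = 95.8, past day 91). At 0.5 a month, 1 of 3, or 2 of 3 with 91 days and a 28-day turnaround (121.6 + 35 = 156.6, past 60.8 + 91 = 151.8). So 33–100% have not finished.

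**The case against.** **'Reached' may mean cleared.** A reader might infer that 10 places open on the day Dose Level 3 opens. The documents do not establish this. Section 4.1 and the synopsis also use the word for the MTD, which can be reached only through DLT data. Opening 10 places at once would also defeat the rule of 3 then 3 more patients at Dose Level 3. Against that, the cleared reading makes the trigger redundant. The word is ambiguous, and the PD trigger does not depend on it.

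**The PD trigger is partly an inference.** No passage says that a pharmacologically active dose is declared from one cohort, Section 8.8 looks across dose levels, and the DRT sees AEs, DLTs, PK and PD together. This stands as context. But no passage makes DRT review or a completed window a condition for opening the expansion.

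**Order of rituximab exposure.** A reader might infer that expansion patients would receive the triple combination before anyone else at that level. On the PD route this does not follow. Each patient receives rituximab on their own study day 7 + 35 + 2 = 44, so an expansion patient who starts after the trigger runs behind the cohort patients who are on schedule.

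**Safeguards exist.** Section 8.4 suspends enrolment for a death not clearly and solely due to disease, for a medically equivalent SAE in more than one patient, and for certain unresolved severe or neurologic events. These are partial. Two patients with different non-fatal, non-neurologic grade 3 DLTs would fail a level without necessarily meeting any criterion. The enrolment pause for 2 or more DLTs is written only for Dose Level 1.

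**The size is soft.** Ten patients at 33%, 40% or 50% would give 3.3, 4.0 or 5.0 expected DLT patients, but only if all ten are dosed, which the slower accrual rates rule out. Using 98 days alone would suggest that 67–100% of the cohort is unfinished; with the stated 91 days the range is 33–100%.

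**Conclusion.** The point holds as a conflict between passages together with a missing condition. As written, Section 4.1 and the synopsis permit up to 10 additional patients on a PD result obtainable up to about 83–90 days, less turnaround, before the latest patient's DLT window closes. Section 5.1.5, Section 8.1 and the synopsis sample-size text place them at the MTD or, in stated cases, lower levels. The lead time rests on the documents' own calendar. The rejection probabilities (0.57–0.83 at Dose Levels 1–2, 0.64–0.89 at Level 3) rest on assumed DLT rates of 33–50%. The roughly 1 to 10 patients exposed rest on assumed accrual and turnaround, and are upper bounds.

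A reader might go further and infer that the trial could recommend a dose that failed its DLT rule. The documents do not support that, because Section 5.1.5 caps the recommended dose at the maximum intended dose or the MTD. The consequence is avoidable exposure and data collected at a level that may be rejected, not necessarily a wrong final dose.

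**What to change.** Reconcile the expansion text in Section 4.1 and the synopsis Study Design with Section 5.1.5, Section 8.1 and the synopsis sample-size paragraph. State that a PD result, or arrival at the maximum planned level, may nominate a level for expansion. The additional patients are enrolled only after that level's escalation patients have completed the DLT period and the level has been cleared under the 3+3 rules in Section 4.1, including the 6-patient rule at Dose Level 3, with DRT review. Reword 'reached' to match.

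The condition should point to the Section 4.1 rules rather than to the fewer-than-2-of-6 definition in Section 5.1.5. The latter would require three more patients at a level already cleared on 0 of 3.

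The 91-day and 98-day windows also need reconciling so that completion of the DLT period has one meaning.

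The cost is a wording change and a delay of up to about three months in opening the expansion. No extra procedures or analyses are needed.

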Patients may continue treatment as long as toxicity remains acceptable, the patient has not withdrawn consent and is deriving clinical benefit in the opinion of the Investigator while receiving study treatment according to the treatment durations specified for the agents in Section [4.4](#). Response and disease progression will be assessed based on the Revised Criteria for Response Assessment of Hodgkin's and Non-Hodgkin's Lymphoma (Lugano Criteria; see [Appendix V](#)), as outlined in the [Schedule of Study Evaluations](#).

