6.7 Tumor Assessment (Cycles 4, 7, 10, 13, 19, 22 and 25)

- Tumor assessment is performed on Day 1 (±14 days) of Cycles 4, 7, 10, 13, 19, 22 and 25. Response to study treatment will be assessed via blood, BM, and imaging (PET/CT), as appropriate. If IV contrast is contraindicated, CT without contrast can be used. For patients with BM disease, BM assessments will be done at Day 1 (±14 days) of Cycles 7, 13 and 25 and if required to confirm CR. For patients who achieve CR, imaging may be omitted and MRD assessment will be completed using flow cytometry and/or molecular techniques.

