6.10 Long-Term Follow-Up

Long-term follow-up can be done remotely (e.g., via telephone, via local practitioner or via review of medical records). After a patient is removed from the study, the patient will be followed until death. If a patient has withdrawn consent from study, then follow-up has to cease on the date when consent for study was withdrawn. Off-treatment data on OS will be updated every 3 months or until death or withdrawal of consent for study participation, whichever occurs first. If a patient is removed from the study due to unacceptable AEs, the event(s) will be followed until resolution or stabilization of the AE. Patients who respond and discontinue study treatment for reasons other than disease progression should have response assessments and survival should be collected every 2 months until disease progression or death, whichever occurs first. After disease progression, data for survival should be collected every 3 months until death or withdrawal of consent for study participation.

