8.7 Efficacy

CR rate will be summarized for the safety and EE patients as the proportion (%) of patients with CR. In addition to presenting the CR rate, its associated exact 95% CI will also be presented.

DOR is defined as the time from the date when criteria for response are met to the date of disease

progression or death due to any cause, whichever occurs first. Patients alive with no disease progression will have their DOR censored at the date of the last clinical assessment. The duration of CR will be summarized by providing the median DOR together with associated 95% CI, using Kaplan-Meier methodology.

ORR will be summarized in number (%) of patients in each category of responses and ORR will be analyzed by using a similar method to the one used for the CR rate. ORR is defined as the number of patients who achieve CR and partial remission (PR) measure per Lugano criteria (see [Appendix V](#)).

Survival data are collected at treatment and follow-up periods. Patients will be followed until death or withdrawal of consent from the study, whichever occurs first.

OS is defined as the number of days from the first day of treatment to the date of death due to any cause. Kaplan-Meier methodology will be utilized.

PFS is defined as the time from the first day of treatment to disease progression or death due to any cause, whichever occurs first. If neither event occurs, PFS will be censored at the date of the last clinical assessment. Kaplan-Meier methodology will be utilized.

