Target nodes/nodal masses, extranodal lesions	Score 4 or 5 with no significant change in FDG uptake from baseline at interim or end of treatment	<50% decrease from baseline in SPD of up to 6 dominant, measurable nodes and extranodal sites; no criteria for progressive disease are met
Non measure lesions	Not applicable	No increase consistent with progression
Organ enlargement	Not applicable	No increase consistent with progression
New lesions	None	None
Bone marrow	No change from baseline	Not applicable
Progressive disease	Progressive metabolic disease	Progressive disease requires at least 1 of the following
Individual target nodes/nodal masses	Score 4 or 5 with an increase in intensity of uptake from baseline and/or	PPD progression:
Extranodal lesions	New FDG-avid foci consistent with lymphoma at interim or end-of-treatment assessment	An individual node/lesion must be abnormal with: LDi >1.5 cm and Increase by ≥50% from PPD nadir and an increase in LDi or SDi from nadir 0.5 cm for lesions ≤2 cm 1.0 cm for lesions >2 cm In the setting of splenomegaly, the splenic length must increase by >50% of the extent of its prior increase beyond baseline (e.g., a 15-cm spleen must increase to >16 cm). If no prior splenomegaly, must increase by at least 2 cm from baseline New or recurrent splenomegaly

Non measured lesions	None	New or clear progression of preexisting nonmeasured lesions
New lesions	New FDG-avid foci consistent with lymphoma rather than another etiology (e.g., infection, inflammation). If uncertain regarding etiology of new lesions, biopsy or interval scan may be considered	Regrowth of previously resolved lesions A new node >1.5 cm in any axis A new extranodal site >1.0 cm in any axis; if <1.0 cm in any axis, its presence must be unequivocal and must be attributable to lymphoma Assessable disease of any size unequivocally attributable to lymphoma
Bone marrow	New or recurrent FDG-avid foci	New or recurrent involvement

Revised Response Criteria (Table Key)

Abbreviations: 5PS, 5-point scale, CT computed tomography; FDG, fluorodeoxyglucose; IHC, immunohistochemistry; LDi, longest transverse diameter of a lesion; MRI, magnetic resonance imaging; PET, positron emission tomography; PPD cross product of the LDi and perpendicular diameter; SDi, shortest axis perpendicular to the LDi; SPD, sum of the product of the perpendicular diameters for multiple lesions.

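### After CR, imaging may be replaced by MRD although progression is defined almost wholly by imaging: duration of CR can be overstated, and the two PFS censoring rules conflict

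*Combined protocol and SAP*

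**What the plan says.** **The waiver.** Section 4.1: "For patients who achieve CR, imaging may be omitted, and minimal residual disease (MRD) assessment will be completed using flow cytometry". Section 6.7: "For patients who achieve CR, imaging may be omitted and MRD assessment will be completed using flow cytometry and/or molecular techniques". The synopsis (Treatment Plan) and Table 17 footnote i carry the same permission. The synopsis and Section 4.1 take the MRD sample from marrow and/or blood. None of the four places requires a negative MRD result, says what follows if MRD turns positive, or says when imaging restarts. MRD has no row in Table 17.

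**The standard for progression.** Section 4.1: "Response and disease progression will be assessed based on the Revised Criteria for Response Assessment of Hodgkin's and Non-Hodgkin's Lymphoma", that is, Appendix V. Its PET column asks for an increase in uptake and/or "New FDG-avid foci consistent with lymphoma at interim or end-of-treatment assessment". Its CT column begins "An individual node/lesion must be abnormal with: LDi >1.5 cm" and adds growth thresholds, spleen length and new lesions. The main row that need not be imaging is marrow in the CT column: "New or recurrent involvement".

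**The analysis.** Section 8.7 on DOR: "Patients alive with no disease progression will have their DOR censored at the date of the last clinical assessment". The same section reports the duration of CR as a Kaplan-Meier median and censors PFS by the same kind of visit. Section 7.3 instead censors PFS at the last tumor assessment that can be evaluated.

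**After treatment stops.** Section 6.10: "Patients who respond and discontinue study treatment for reasons other than disease progression should have response assessments". These take place every 2 months, with no modality stated.

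**The concern.** The patients who may be excused from scans are those whose duration of CR is reported. Blood or marrow MRD reflects circulating and marrow disease; it can neither meet nor exclude the nodal and extranodal criteria of Appendix V. A nodal relapse in an unscanned patient is therefore dated when it becomes clinically apparent, or is not recorded at all. If an MRD-only visit counts as a clinical assessment under Section 8.7, the unscanned time is credited as progression-free. A median duration of CR obtained this way could not be compared with a scan-based figure.

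Section 6.10 leaves a related gap. A patient with stable disease who stops treatment for another reason has an end-of-treatment disease assessment, but no scheduled response assessment after it.

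**Working it through.** The plan gives no DOR or PFS figure to reproduce, and the synopsis says that no power calculation was made. The one derived number nearby, the sample size, reproduces (3 × 6 + 10 + 2 × 10 = 48) and does not depend on this point.

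**1. Longest gap.** Inputs: 7-day lead-in, Cycle 1 of 35 days, later cycles of 28 days (Section 4.1); assessments at Cycles 4, 7, 10, 13, 16, 19, 22 and 25 (Table 17).
- Cycle 4 Day 1 = 7 + 35 + 2 × 28 + 1 = study day 99.
- Cycle 25 Day 1 = 7 + 35 + 23 × 28 + 1 = study day 687.
- Gap = 687 − 99 = 588 days = 7 × 84 days, or 588 / 30.4375 = 19.3 months, with 7 assessments after the first.

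Section 6.7 omits Cycle 16, which leaves 6 later assessments and a 168-day interval from Cycle 13 to Cycle 19.

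**2. Effect on duration of CR (illustrative).** The documents give neither relapse times nor detection lags, so both are assumed. T, the time from CR to nodal relapse, is exponential with median 3, 6 or 11 months. L, the lag to clinical detection, is exponential with mean 1, 3 or 6 months.
- Scans kept: relapse dated at min(84 × ceil(T/84), T + L), in days.
- All scans waived: relapse dated at T + L.

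Median duration of CR in months from 200,000 simulated patients, kept vs waived:

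| True median | Mean lag 1 | Mean lag 3 | Mean lag 6 |
|---|---|---|---|
| 3 | 3.5 vs 4.1 | 4.1 vs 6.1 | 4.6 vs 8.6 |
| 6 | 6.7 vs 7.1 | 7.5 vs 9.3 | 8.3 vs 12.2 |
| 11 | 11.0 vs 12.0 | 11.0 vs 14.2 | 11.0 vs 17.6 |

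The differences run from 7.1 − 6.7 = 0.4 to 17.6 − 11.0 = 6.6 months. In the last row the scan-based median stays at 11.0 because a scan falls at 4 × 84 = 336 days = 11.0 months. Mean dating delay is about 0.7 to 1.3 months with scans and 1 to 6 months without.

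With follow-up ended 588 days after CR, true median 6 and mean lag 3, the Section 8.7 reading gives 7.4 vs 9.2 months. If 25% of relapses are never detected, the waived figure becomes 12.9.

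**3. PFS, Section 8.7 rule, whole cohort.** Further assumptions: CR documented 98 days after first dose, true median duration of CR 6 months, mean lag 3 months, median PFS 3 months without CR.

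| CR share | Median PFS, months, kept vs waived | 12-month PFS, kept vs waived |
|---|---|---|
| 10% | 3.5 vs 3.5 | 9.5% vs 11.0% |
| 20% | 4.2 vs 4.2 | 12.7% vs 15.6% |
| 40% | 6.0 vs 6.2 | 19.0% vs 24.8% |

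**4. PFS, Section 7.3 rule.** This was simulated in CR patients, in months from CR, with mean lag 3. An unscanned patient with no detected relapse is censored back at the CR scan, which shortens the estimate. A clinically detected relapse is still dated late, which lengthens it. Kept vs waived medians are 4.1 vs 5.9, 7.4 vs 7.8 and 11.0 vs 9.2 for true medians 3, 6 and 11. The sign changes, so this censoring rule does not by itself remove the bias.

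**The case against.** The waiver is optional, and patients in CR are not left unobserved. Physical examination is scheduled on Day 1 of every cycle; Table 17 footnote e makes only the two-dimensional node and organ measurement optional. From Cycle 2, serum chemistry with LDH is drawn on Days 1, 8 and 15. A disease assessment is planned at end of treatment, and responders who stop without progression are assessed every 2 months. Appendix V also allows non-measured lesions found by palpation. All of this stands and limits the delay, but it does not replace the nodal imaging criteria.

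Four stronger readings are tempting and are not supported:
- **That DOR and PFS are certainly overstated.** The bias depends on how often the waiver is used. Section 8.7 does not define a clinical assessment, so counting an MRD-only visit is a plausible reading rather than stated text. For PFS, Section 7.3 gives a different rule under which the direction varies.
- **That 588 days measures the bias.** It requires CR at the first assessment, every later scan waived, and follow-up through Cycle 25.
- **That keeping scans dates relapse to within 12 weeks.** That follows Table 17. Section 6.7 leaves a 24-week interval, and its windows are ±14 days.
- **That progression in stable-disease patients is never recorded.** The synopsis asks patients withdrawn from treatment to complete scheduled follow-up visits, and Section 6.10 allows contact with local practitioners and record review. Capture is unsystematic rather than absent, and the documents do not establish the direction of any resulting bias.

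**Conclusion.** The point holds in limited form. The plan lets MRD stand in for imaging after CR while defining progression almost wholly by imaging. Where sites use the waiver, nodal relapse can be missed or dated late, and the reported duration of CR can be overstated under Section 8.7. The 0.4 to 6.6 month range assumes that every scan after CR is waived and rests on assumed relapse and lag times; it shows direction and scale only.

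For PFS, the defect is the conflict between Sections 7.3 and 8.7. Overstatement follows under 8.7, but the whole-cohort median moves little if few patients reach CR. Under 7.3 the direction is not fixed. The limit on off-treatment response assessments in Section 6.10 is a smaller, separate gap in PFS capture.

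DOR and PFS are secondary and descriptive. The MTD, the recommended dose and the sample size are unaffected. The change should be made, but the trial's primary purpose does not hang on it.

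**What to change.** 1. In the synopsis, Section 4.1, Table 17 footnote i and Section 6.7, remove the waiver for patients counted in DOR and PFS. Keep CT or PET/CT every 3 cycles until progression, with MRD as an addition. Reconcile Table 17 and Section 6.7 on Cycle 16.
2. In Sections 7.3 and 8.7, use one rule: censor DOR and PFS at the last evaluable Appendix V tumor assessment, and state that an MRD-only visit is not one. If the waiver is kept, add a sensitivity analysis for CR patients without scans, because censoring alone does not remove the bias.
3. In Section 6.10 and the synopsis, apply the 2-monthly response assessments to all patients who discontinue without progression, not only responders.

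Cost: protocol and analysis wording, up to 7 more scans for a long-term CR patient (6 if Cycle 16 is dropped), some added scans in stable-disease patients, and slightly shorter reported follow-up.
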